## 16.6 Analysis of secondary efficacy endpoints

### 16.6.1 Number of confirmed UTIs

The number of confirmed UTIs for both the:

- Mean number of confirmed UTIs during the three months' intervention period, as compared to placebo.

and

- Mean number of confirmed UTIs during the three months' follow-up period, as compared to placebo.

will be analysed using the same methods as for the primary endpoint.

### 16.6.2 Time to first relapse of UTI

Time to first relapse of UTI will be defined as the time from delivery of intervention (*i.e.* start of intervention) to date of first confirmed UTI ((Confirm date – Intervention date) + 1).

Subjects with no UTI will be censored at last known date within the study period.

The time to first relapse will be analysed using Cox regression analysis and presented by Kaplan-Meier graphs.

### 16.6.3 Relapse rate

The relapse rate for both:

- Proportion of subjects (%) who experienced at least one confirmed UTI during three months from start of intervention, as compared to placebo.

and

- Proportion of subjects (%) who experienced at least one confirmed UTI during six months from start of intervention, as compared to placebo.

will be analysed using Chi-square test without continuity correction and presented using frequency tables.

## **16.7 Analysis safety endpoints**

### **16.7.1 Adverse Events**

Adverse Events and SAEs will be recorded from start of IP intervention. Medical events occurring between screening and start of IP intervention will be reported separately.

## **16.8 Statistical/analytical issues**

### **16.8.1 Adjustments for covariates**

History of UTIs, age, and sexual activity will be used as covariates in the analysis of mean number of UTIs.

### **16.8.2 Handling of dropouts or missing data**

No imputation of missing data will be performed.

### **16.8.3 Multi-centre studies**

No adjustment for centre will be applied, since this will not be considered as a multi-centre study.

### **16.8.4 Multiple comparison/multiplicity**

All statistical significant findings need to be interpreted from a medical perspective and judged as clinical relevant or not and therefore no adjustment for multiplicity will be performed.

### **16.8.5 Examination of subgroups**

To be addressed in the SAP.

### **16.8.6 Interim analyses**

No interim analysis will be performed.

## 17.2 Declaration of Helsinki

[http://www.up.ac.za/media/shared/Legacy/sitefiles/file/45/2875/declarationofhelsinki\\_fortaleza\\_brazil\\_2013.pdf](http://www.up.ac.za/media/shared/Legacy/sitefiles/file/45/2875/declarationofhelsinki_fortaleza_brazil_2013.pdf)

1 VERSION HISTORY

This Statistical Analysis Plan (SAP) for study BioGaia CSUB 0144 is based on the protocol dated 24OCT2017.

Table 1 SAP Version History Summary

SAP version	Approval Date	Changes	Rationale
1	08AUG2019	NA	Original version
2	xxAUG2019		

2 INTRODUCTION

This Statistical Analysis Plan (SAP) gives details regarding the statistical analyses and data presentation outlined in the final Clinical study protocol (CSP) for the study BioGaia CSUB 0144. Any changes from the final CSP are given in Section 0.

3 CLINICAL STUDY DETAILS

3.1 Clinical Study Objectives and Endpoints

Objects	Estimands/Endpoints
Primary	
 The primary objective is to evaluate the effect of oral supplementation with Lactobacillus reuteri on the frequency of confirmed UTI during six months from start of intervention in adult women with recurrent UTI.
Secondary	
 Mean number of confirmed UTIs during six months from start to intervention, as compared to placebo. To evaluate the effect of oral supplementation with Lactobacillus reuteri on the frequency of confirmed UTI during the three months' intervention period and during the three months' follow-up period, respectively. To evaluate the effect of oral supplementation with Lactobacillus reuteri on time to first relapse of UTI. To evaluate the effect of oral supplementation with Lactobacillus reuteri on relapse rate at three and six months after start of intervention. To assess the tolerability of oral supplementation with Lactobacillus reuteri in adult women with recurrent UTI.
Tertiary/Exploratory	
 Not applicable

Objective	Statistical Category	Estimand ¹	Variable/ Endpoint	Population	IES ¹	PLS ¹ (Analysis)
Clinical Category						
New episode of UTI	Primary/MCP	Change from baseline in number of confirmed UTI at three and six months.	FAS	Initiation of rescue medication: "had rescue medication not been initiated" (hypothetical).	Mean difference between interventions (LSMD from CFB ANCOVA with MI from participants from same randomized arm off-treatment at three to six months)	
Sensitivity				Discontinuation of treatment due to adverse event (AE): "regardless of treatment discontinuation due to AE" (treatment policy)	(LSMD from CFB ANCOVA with reference-based MI)	
Supplementary		Number of confirmed UTI responder (criterion) and rescue medication not initiated at three and six months and remained adherent to intervention	FAS	Captured in variable definition (composite)	Odds ratio between interventions (Logistic regression)	
Secondary/MCP						
Number of confirmed UTI	Secondary					
Time from start of intervention to relapse of UTI	Tertiary Exploratory					

Secondary Objective: 1. To evaluate the effect of oral supplementation with *Lactobacillus reuteri* on the frequency of confirmed UTI during the three months' intervention period and during the three months' follow-up period, respectively.

Objective	Statistical Category	Estimand ^a	Variable/ Endpoint	Population	IES ¹	PLS ¹ (Analysis)
2. To evaluate the effect of oral supplementation with Lactobacillus reuteri on time to first relapse of UTI.						
3. To evaluate the effect of oral supplementation with Lactobacillus reuteri on relapse rate at three and six months after start of intervention.						
4. To assess the tolerability of oral supplementation with Lactobacillus reuteri in adult women with recurrent UTI.						
AEs	Presence of TEAEs	Safety				Record from start of IP intervention. Medical events occurring between screening and start of IP intervention.
SAEs		Safety				Record from start of IP intervention. Medical events occurring between screening and start of IP intervention.
		Safety				Record from start of IP intervention. Medical events occurring between screening and start of IP intervention.

IES = Intercurrent event(s) strategy; PLS = Population-level summary.

CFB = Change From Baseline

LSMD = Least Squares Mean Difference

FAS = Full Analysis Set

TEAE = Treatment Emergent Adverse Event

MCP = Multiple comparisons procedure: FWER controlled for hypothesis testing of selected endpoints as specified in Section <cross-reference>.

¹ All estimand attributes explicitly identified for primary/secondary and selected key estimands only.

3.2 Clinical Study Design

A double-blinded, randomized, placebo-controlled, parallel-group study. The study will be performed in female subjects aged 18-50 since this is the population expected to benefit from the intervention studied. The study structure based on assessments using video -and phone-calls to ensure access to a broad population in a wide area although only one study site will be involved. No clinical safety assessments are considered necessary considering the general good safety profile of probiotics.

3.3 Statistical Hypotheses

Hypothesis:

H_0 : Mean number of UTIs in Probiotic group = Mean number of UTIs in the placebo group.

H_1 : Mean number of UTIs in Probiotic group \neq Mean number of UTIs in the placebo group.

3.4 Number of Subjects

The number of subjects needed to verify that the mean number of UTIs during six months for the probiotic will be 0.75 and for placebo 1.35 with a common standard deviation of 1.15, will be 118 (1:1 randomization) using a significance level of 5% and a power of 80%.

Assuming a drop-out rate of 15% a total of 140 subjects will be included, 70 in each intervention arm.

3.5 Methods of Assigning Subject to IMP

The study will consist of a combined screening and randomization assessment, an IP first dose confirmation call and monthly follow up assessments for six months. The screening and randomization assessment will be performed as a phone call or a video-call using an e-health digital platform. Informed consent will be signed via Bank ID. The monthly follow-up assessments will be performed either as a video-call or by phone. However, physical visits to the clinic at CTC AB might be performed for subjects in Uppsala.

Subjects will be recruited from advertising (e.g in social media, at pharmacies etc.). The subjects will contact the study site by phone or e-mail. Brief oral information about the study will be given and pre-defined pre-screening questions will be asked. Written information will be sent to the subjects qualified for screening together with instructions regarding the e-health platform and Bank ID signing procedures.

During the screening and randomization assessment, full information about the study will be given and informed consent. Information regarding demographics, weight, height, medical history, UTI history, medication history, use of restricted products, and pregnancy will be collected and diet restrictions. Subjects will be screened for eligibility as per the pre-defined eligibility criteria.

Eligible and consenting subjects will be randomized to intervention with either *Lactobacillus reuteri* or placebo. The subject will be provided with Investigational Product (IP) for three months (90 days) and niture/Leu urine test kits. Instructions to start intake of IP as soon as the IP has been picked-up will be given. The subject will be contacted by study staff 1-3 days after randomization to confirm that first IP dose has been taken.

At the monthly assessments (video-call/phone-call or visit), the subject will be asked to answer predefined questions regarding symptoms (frequency, urgency and dysuria). If two out of three symptoms are present a UTI is confirmed. If only one symptom is present the subject will perform a niture/Leu urine test at home, preferably on urine retained in the bladder for approximately 3 hrs. If the test is positive (one of two analyses), a UTI is confirmed and the subject is recommended to contact the health care system for consultation regarding antibiotic treatment. Information on AEs, concomitant medications, use of restricted products, pregnancy, and compliance with instructions for IP intake will be collected.

An electronic diary will be used by the subject during the study period for recording of occurrence of UTI symptoms and sexual activity (frequency of intercourse, new partner, use of condom with spermicide).

The monthly follow-up assessment after six months will be the final study assessment. Number of empty sachets and any unused IP will be reported to CTC AB by the subject and documented by site staff on the IP accountability list.

3.6 Blinding

This is a double-blinded study. All study staff, including the Principal Investigator and the persons performing the subject assessments using the video link or phone calls, will be blinded during the study. Sealed individual treatment code envelopes will be kept at the clinic to be able to break the code if any emergency occurs, as judged by the Investigator.

4 STATISTICAL AND ANALYTICAL PLANS

4.1 Sample Size Determination

A total of 140 subjects completed will be required, 70 in each intervention arm.

4.2 Definition of Analysis Sets

4.2.1 Full Analysis Set

The Full Analysis Set (FAS) will consist of all subjects who have been randomized and received at least one dose of Intervention.

4.2.2 Per Protocol Analysis Set

The Per Protocol Set (PPS) will consist of all subjects who have been randomized, completed the three months of intervention period and without any major protocol deviations. All deviations will be presented and discussed at the clean file meeting. If the compliance with the IP regimen should be below 80% the subject will not be included in the PPS population. The definition of compliance by calculating the number of days in the study (90 days) in relation to number of unused IP as reported by the subject.

$$\frac{90 \text{ days} - \text{number of doses unused}}{\text{study length with a maximum of 90 days}} \geq 0.80$$

Calculations for compliance will be used on visit 4 (3 month).

Subjects who have been used prohibited medications, long term antibiotics or Hipex during the study will be excluded from PPS.

Subjects not participated at visit 4 and 7 (3 month and 6 month) will not be included in the PPS population.

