## **11.4 Dispensing and accountability**

The IP will be picked-up by the subject at local IP distribution sites. The subject will receive 90 packages of IP. The IP can be picked-up at several occasions, if preferred by the subject. At the last assessment of the intervention period (Day 90), the subject will inform CTC AB about the number of empty sachets and any unused IP for accountability and check of intervention compliance.

Each IP distribution site will maintain an IP accountability list detailing the dates and quantities of the IP allocated to each subject. Clinical staff will record any unused IP on the IP accountability list, based on information given by the subject.

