### **16.3.2 Per Protocol Set**

The Per Protocol Set (PPS) will consist of all subjects who have been randomized, completed the three months of intervention period and without any major protocol deviations. All deviations will be presented and discussed at the clean file meeting. If the compliance with the IP regimen should be below 80% the subject will not be included in the PPS population. The definition of compliance is by calculating the number of delivered products in relation to the number of unused IP as reported by the subject.

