### **16.4.4 Compliance with the intervention**

Compliance with the intervention will be calculated as number of delivered products divided by number of reported unused products and presented using summary statistics.

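### Compliance is mis-specified twice: the protocol ratio for the descriptive summary can never fall below 100%, and the SAP per-protocol formula overstates intake if a woman has not collected all 90 packages

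*SAP*

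**What the plan says.** **Protocol.** Section 16.4.4 states: "Compliance with the intervention will be calculated as number of delivered products divided by number of reported unused products". Section 16.3.2 relates the same two counts more loosely and attaches the per-protocol rule: "If the compliance with the IP regimen should be below 80% the subject will not be included in the PPS population". Section 11.4 plans 90 packages per woman but adds: "The IP can be picked-up at several occasions, if preferred by the subject". The same section has each distribution site list the dates and quantities handed out, and has the woman report empty sachets and unused product at Day 90.

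**SAP.** Section 4.2.2 keeps the 80% cut but redefines compliance as "calculating the number of days in the study (90 days) in relation to number of unused IP as reported by the subject". The displayed formula makes this precise: the numerator is 90 minus the doses unused, and the denominator is "study length with a maximum of 90 days". It is evaluated at visit 4. Section 8 lists the compliance definition for the PPS as a change from the protocol. It says nothing about the descriptive summary in protocol 16.4.4. SAP 6.1 covers start, stop and duration of intake but gives no compliance measure. Under SAP 4.2.3 the full analysis set (FAS) serves the primary and secondary objectives and safety; the PPS serves the secondary efficacy evaluations only.

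**The concern.** A compliance measure should be doses taken over doses due. Neither formula is built that way.

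The protocol ratio has unused product in the denominator. It is therefore not a percentage of anything taken, and it has no value for a woman who took every dose.

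The SAP formula puts a fixed 90 where the quantity received should be. That is harmless if every woman collects 90 packages. If she collects fewer, 90 minus unused is no longer the number of doses taken, because a package she never held may not appear among those she reports as unused.

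Two things are at stake. The PPS is meant to show the effect in women who took the product, and the 80% rule is its only numerical intake criterion. The descriptive compliance summary would also carry figures that cannot be read as adherence.

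**Working it through.** **Inputs.** Planned supply of 90 packages and staged pick-up (protocol 11.4); ratio of delivered to unused (protocol 16.4.4); numerator 90 minus unused, denominator min(study length, 90), cut 0.80 (SAP 4.2.2); visit 4 at Day 90±7 (protocol Table 9.1). Let C be packages collected, U packages reported unused, and L study length at visit 4. The reference value is (C − U)/min(L, 90).

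**1. Protocol ratio, C/U.** Since U cannot exceed C, the ratio is at least 1. With C = 90:

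| Unused | Doses taken | Protocol ratio |
|---|---|---|
| 0 | 90 (100%) | 90/0, undefined |
| 18 | 72 (80%) | 90/18 = 500% |
| 45 | 45 (50%) | 90/45 = 200% |
| 81 | 9 (10%) | 90/81 = 111% |
| 90 | 0 (0%) | 90/90 = 100% |

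**2. SAP formula in the planned case, C = 90.** Here 90 − U equals C − U, so the SAP value and the reference are identical.
- 18 unused: 72/90 = 80.0%, included. 19 unused: 71/90 = 78.9%, excluded.
- Day 83, 24 unused: 66/83 = 79.5% on both.
- Day 97, 18 unused: 72/90 = 80.0% on both.
- Across all 91 possible unused counts at L = 90, PPS status never differs.

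**3. SAP formula when C < 90, uncollected packages not reported as unused.** The numerator is too large by exactly 90 − C. With L = 90:

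| Collected | Unused | SAP value | Reference |
|---|---|---|---|
| 60 | 0 | 90/90 = 100% | 60/90 = 66.7% |
| 60 | 10 | 80/90 = 88.9% | 50/90 = 55.6% |
| 30 | 0 | 90/90 = 100% | 30/90 = 33.3% |
| 30 | 15 | 75/90 = 83.3% | 15/90 = 16.7% |

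All four pass the SAP rule and fail the reference.

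The range that is misclassified follows from the cut. The SAP rule passes when U ≤ 18; the reference passes when C − U ≥ 72.
- 80 collected: 9 to 18 unused is wrongly passed.
- 72 collected: 1 to 18 unused.
- 71 or fewer collected: every report of 0 to 18 unused.

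**4. Values above 100%.** These can arise inside the visit window, but only with partial collection: 60 collected, 0 unused, day 83 gives 90/83 = 108.4% against 60/83 = 72.3%.

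**The case against.** The strongest reply is that the SAP formula works as planned. The protocol states a supply of 90, staged pick-up concerns timing, and nothing says that packages left at the distribution site are omitted from the unused count. If they were counted as unused, the formula would be right in every case. This stands as a limit: the SAP error is conditional, and its frequency is unknown. It does not remove the point. The count is reported by the woman, and protocol 11.8 has her destroy and report unused product, so product in her own hands is the natural reading.

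A reader might also infer three stronger things that the documents do not support.

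- *The 80% rule excludes nobody.* That is true of the protocol ratio taken literally, but SAP 4.2.2 replaced it for the PPS and SAP section 8 declares the change. Under the rule in force, a woman who collected everything and reaches day 90 is excluded at 19 or more unused.
- *Early leavers are inflated because only the denominator is shortened.* With 90 collected the numerator adjusts itself: leaving at day 45 after 35 doses leaves 55 unused, and (90 − 55)/45 = 78%, the true value. A day-45 leaver also fails the PPS requirements to complete the intervention and to attend visits 4 and 7.
- *Women with poor intake are certain to remain in the PPS.* Intake is asked about monthly (protocol 11.7), and major deviations, reviewed at the clean file meeting, also exclude. Some such women could be caught there, although these routes set no numerical threshold.

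**Conclusion.** Both defects are in the text, with different force.

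The protocol 16.4.4 ratio is wrong without any assumption: it is undefined at full adherence and bounded below by 100%. It does not decide PPS membership, but it remains the only definition for the descriptive compliance summary.

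The SAP formula is right for a woman who collected all 90 packages. Otherwise it overstates doses taken by the number not collected, on the assumption that these are not reported as unused. For an individual woman the error can be large (100% against 67% or 33%). The number of women affected cannot be derived from the documents, and no effect on an efficacy estimate can be claimed. The consequence is confined to the PPS, hence to secondary efficacy evaluations. The FAS and the primary analysis are unaffected.

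The correction is worth making because it is cheap and uses quantities already recorded.

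**What to change.** Use one definition for both the 80% rule and the compliance summary:

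(packages collected − packages reported unused) / min(study length at visit 4, 90)

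Packages collected come from the distribution-site accountability list. Correct protocol 16.3.2 and 16.4.4 to match, and extend the entry in SAP section 8 so that it covers the descriptive summary as well as the PPS.

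Keep the SAP denominator. If it ran only to the last day of intake, a woman who took 30 doses and stopped at day 30 would score 30/30 = 100%, including one who had collected all 90 and whom the present formula correctly scores at 30/90 = 33%.

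Cost: one changed term in the SAP formula and matching text in two protocol sections. No new data are needed. Nothing changes for women who collected all 90 packages. The PPS may become slightly smaller.

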### 10.6.2 Prior and concomitant therapy

No probiotic food supplements, probiotic foods or fermented food other than the test product, including vaginal products containing *Lactobacillus* (including probiotic tampons) or affecting the pH, are allowed from screening and throughout the study period.

Neither is any food or food supplements containing cranberries allowed from screening and throughout the study period. Subjects should continue with the same general diet and lifestyle, except probiotic and cranberry consumption.

Use of spermicide contraceptives including spermicidal condom will not be allowed during the study, up to Day 180.

Use of oral or vaginal fungicides will not be allowed during the study, up to Day 180. If typical vaginal candida symptoms appear (itching and typical thick, clumpy, white vaginal discharge) sporadic usage of oral fluconazole 150 mg as a single dose may be allowed and should be noted.

Subjects must not participate in any other clinical interventional study during the study period.

Other medications considered necessary for the subject's safety and well-being, may be used during the study period. In case of antibiotic use, the type and duration should be recorded. Any use of fluconazole, prohibited medication, therapies or products will require evaluation by the Investigator to determine whether or not the subject should continue in the study. This may be done in consultation with the Sponsor.

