### 16.1 General

Data on continuous variables will be presented using summary statistics. Data will be presented in terms of number (N), arithmetic mean, standard deviation (SD), minimum and maximum value.

Categorical data will be presented as counts and percentages. Individual subject data will be listed by randomization number, and where applicable by assessment time.

All statistical tests will be performed using a two-sided hypothesis with a significance level of 5%.

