4.2.3 Use of analysis set

The FAS population will be used for both of efficacy (primary objectives and secondary objectives) and safety evaluation and the PPS will only be used for the efficacy (i.e. secondary objectives) evaluations.

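### One Per Protocol Set with exclusions running to Day 180 can remove women from the three-month and first-relapse analyses for events that came after those endpoints were complete

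*SAP*

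**What the plan says.** - **Medication rule, SAP 4.2.2:** "Subjects who have been used prohibited medications, long term antibiotics or Hipex during the study will be excluded from PPS". The window is the whole study, and protocol Table 9.1 runs to Day 180.
- **Attendance rule, SAP 4.2.2:** "Subjects not participated at visit 4 and 7 (3 month and 6 month) will not be included in the PPS population". Visit 4 is Day 90 and Visit 7 is Day 180. The sentence does not say whether missing either visit excludes, or only missing both.
- **Use of the set, SAP 4.2.3:** "the PPS will only be used for the efficacy (i.e. secondary objectives) evaluations". The first half of that sentence gives the FAS to the primary and secondary objectives and to safety.
- **Secondary efficacy endpoints, SAP 7.2.1:** three-month count, follow-up-period count, time to first relapse, three-month relapse and six-month relapse. There is no six-month count among them; that is the primary endpoint.
- **Protocol PPS, section 16.3.2:** women who were "randomized, completed the three months of intervention period and without any major protocol deviations", with at least 80% compliance. It has no Day 180 attendance rule. SAP section 8 openly lists both new rules as changes.
- **Protocol 10.6.2:** other necessary medication may be used. "In case of antibiotic use, the type and duration should be recorded".
- **SAP 7.1:** announces an additional primary analysis that includes users of the excluded medications. This implies that the main primary analysis leaves them out, although 4.2.3 assigns it to the FAS, which has no such exclusion.

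**The concern.** A per-protocol exclusion should rest on what happened before or during the period in which the endpoint is measured. Here it can rest on what happened afterwards. Two cases show it.

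- A woman takes the product for 90 days, has confirmed UTIs on Days 30 and 80, and starts a long-term antibiotic or Hiprex on Day 120. Her three-month count, three-month relapse status and time to first relapse were all settled by Day 90, yet she leaves the PPS for all three.
- A compliant woman relapses on Day 40, attends Visit 4 and is lost on Day 130. If missing either visit excludes, she leaves the three-month analyses for missing Visit 7.

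All participants have recurrent UTI, so it is plausible that long-term antibiotics or Hiprex follow further UTIs. Membership of the PPS would then depend on the outcome being compared. A PPS result that differs from the FAS result could be misread as the effect of adherence when it is partly selection.

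**Working it through.** **Plan's own figure.** Two-sided 5%, power 80%, SD 1.15, difference 1.35 − 0.75 = 0.60 (SAP 3.4: "mean number of UTIs during six months for the probiotic will be 0.75 and for placebo 1.35"). n per arm = 2(1.960 + 0.842)² × 1.15² / 0.60² = 57.7, so 58; the exact t calculation gives 59, or 118 in total, as stated. 118/0.85 = 139, which the plan rounds to 140. The documents give no figure for the PPS, so the rest is illustration.

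**Assumptions.** Poisson counts, spread evenly, independent between the two halves. Three-month means: λ = 1.35/2 = 0.675 (placebo) and 0.75/2 = 0.375 (test). A share s of women whose third UTI falls after Day 90 start an excluded product, with the same s in both arms. This isolates exclusions triggered after the three-month endpoints are complete.

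**Formulas.** N1 and N2 are the counts in months 1–3 and 4–6; p0, p1, p2 are the Poisson probabilities of 0, 1 and 2.
- Share whose third UTI falls after Day 90: X = p0·P(N2≥3) + p1·P(N2≥2) + p2·P(N2≥1)
- Their contribution to the three-month mean: A = p1·P(N2≥2) + 2·p2·P(N2≥1)
- Three-month mean in women kept: (λ − sA)/(1 − sX)
- Three-month relapse in women kept: 1 − p0[1 − s·P(N2≥3)]/(1 − sX)

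**Values.**
- Placebo: p0 = 0.509, p1 = 0.344, p2 = 0.116, P(N2≥3) = 0.031; X = 0.123, A = 0.164.
- Test: p0 = 0.687, p1 = 0.258, p2 = 0.048, P(N2≥3) = 0.007; X = 0.034, A = 0.044.

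**Results, placebo v test.**

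| s | Excluded | Three-month mean | Difference | Three-month relapse | Difference |
|---|---|---|---|---|---|
| 0 | 0 v 0 | 0.675 v 0.375 | 0.30 | 49.1% v 31.3% | 17.8 points |
| 0.25 | 3.1% v 0.8% | 0.654 v 0.367 | 0.29 | 47.9% v 30.8% | 17.1 points |
| 0.5 | 6.2% v 1.7% | 0.632 v 0.359 | 0.27 | 46.6% v 30.3% | 16.3 points |
| 1 | 12.3% v 3.4% | 0.582 v 0.342 | 0.24 | 43.7% v 29.3% | 14.4 points |

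Simulating the same model, the six-month hazard ratio for first relapse goes from 0.56 to 0.57 (s = 0.5) and 0.59 (s = 1).

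**Other mechanisms.**
- *Each UTI in either period leads to exclusion with probability 10%, 20% or 30%.* Poisson: three-month mean difference 0.27, 0.24, 0.21; hazard ratio unchanged at 0.56. With counts that vary more between women (gamma frailty, shape 1): 0.22, 0.17, 0.12, and six-month hazard ratio from 0.66 to 0.67, 0.68, 0.69.
- *Only follow-up UTIs lead to exclusion, same probabilities.* Without frailty the three-month difference stays at 0.30, because the halves are independent. With frailty it becomes 0.27, 0.25, 0.22.
- *Exclusion unrelated to UTIs.* No effect measure changes; only precision is lost.
- *Exclusion in one arm only (table model, s = 1).* Test arm only: 0.675 − 0.342 = 0.33, larger than 0.30. Placebo arm only: 0.582 − 0.375 = 0.21.

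**The case against.** The strongest reply is that the FAS analyses of every primary and secondary endpoint keep these women, so no conclusion need rest on the PPS. That stands, and it limits the point to supporting analyses.

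Three stronger readings are tempting, and the documents do not support them.

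- **That the effect will shrink.** The documents give no switching rate, cause or split by arm. Shrinkage of absolute differences follows only if exclusion follows UTIs at similar rates in both arms. The hazard ratio may barely move, and unequal switching could push the result the other way.
- **That the primary result is biased in the same way.** The six-month mean count is not assigned to the PPS by SAP 4.2.3. The wording of SAP 7.1 makes the matter unclear, which calls for clarification; it does not show a bias.
- **That the SAP excludes women for antibiotics the protocol permits, so that most treated relapses would lead to exclusion.** SAP 4.2.2 names long-term antibiotics, not ordinary courses for a relapse, and current long-term antibiotic treatment is already an entry exclusion in protocol 10.5. A treatment can be permitted on study and still be a reason to leave a per-protocol set.

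It can also be said that the protocol PPS already barred major deviations without a time limit, while some restrictions run to Day 180, so later deviations could have excluded women before the SAP was written. That is fair. What the SAP adds is an automatic exclusion whatever the timing, and the Visit 7 condition.

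**Conclusion.** The point holds as a fault in the definition of a supporting analysis. As written, the PPS conditions on events after the three-month endpoints and after first relapse, and nothing elsewhere in the SAP limits the exclusion to the endpoint's own window. The attendance sentence is ambiguous, and neither reading suits every endpoint: missing either visit removes women with complete three-month data, while missing both as the test lets a woman without a Day 180 assessment stay in the follow-up-period count.

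The size is not known from the documents. With the plan's means, Poisson counts and equal switching after a third UTI beyond Day 90, the three-month mean difference would be 0.24 to 0.29 instead of 0.30, and the three-month relapse difference 14.4 to 17.1 points instead of 17.8, for shares from all down to a quarter. The upper share is deliberately extreme. The fault is worth correcting because the correction is cheap and the direction of any bias cannot be known in advance.

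**What to change.** Amend SAP 4.2.2 so that PPS membership is set per endpoint.

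- **Three-month relapse, six-month relapse, time to first relapse:** treat a prohibited product, long-term antibiotic or Hiprex as an exclusion only if it started before the woman's first confirmed UTI and within the endpoint's window. SAP 4.12 dates site-registered UTIs by telephone contact, so state how near-ties are ordered.
- **Three-month count:** consider only deviations up to Day 90. A woman who relapses early and switches before Day 90 is still removed, so some outcome-driven exclusion remains; state that the FAS result leads.
- **Attendance:** replace the joint Visit 4 and 7 condition with the visit each endpoint needs. Drop Visit 7 for the three-month endpoints and for women who have already relapsed; require it for the follow-up-period count. Time to first relapse needs no Visit 7 condition, since SAP 7.2.1.2 censors at the last known date. For six-month relapse, requiring Visit 7 only of women without a relapse raises the proportion in both arms, so read it beside the Kaplan-Meier estimate.
- **SAP 7.1 and 4.2.3:** say which analysis set the main primary analysis uses, and what the additional analysis adds.
- **Timing:** fix all PPS flags before the code is broken.

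The cost is SAP wording and up to three PPS flags, using medication and UTI dates from data already collected. The downside is a PPS whose size differs by endpoint.
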